1. VERSION HISTORY

This CSR Statistical Analysis Plan (SAP) for study **C0221002** is based on **Protocol Amendment 5** dated **18-Aug-2021**.

Table 1. Summary of Changes

Version/ Date	Associated Protocol Amendment	Rationale	Specific Changes
2 08 FEB 2023	5 18 Aug 2021	Updates to minor components of analysis due to recent FDA guidance, CCI	
 • CCI [REDACTED] • further clarification on analysis and presentation of multiple dose levels; • inclusion of robust standard error estimation included in SAS code due to updated FDA guidance on controlling for covariates in randomized controlled trials; • update sample SAS code due to incorrect coding in previous version; • update to language on missing values being imputed by MMRM; • CCI [REDACTED]
2 08 FEB 2023	5 18 Aug 2021	Changes needed based on Protocol Amendment 5	
 • Updated study objectives, study design and statistical methods to extend treatment duration from 12 weeks to 24 weeks, and to add an optional cohort (Cohort 3) to potentially explore a higher dose of PF-06730512 CCI [REDACTED] in subjects with FSGS, based on emerging data from the study.
2 08 FEB 2023	4 12 Jun 2020	Changes needed based on emerging data to incorporate into IA1 and align with current IA Charter	
 • Included PPAS analysis into IA readouts due to emerging discontinuations in the study (Section 4.2, 6.1.1.2 and Appendix 1.1). • Added predictive probability table related to first morning void sensitivity analysis as was required based on IA Charter (version 1.0) (Section 6.1.1.2 and Appendix 1.1). • Added safety summaries that may be required at IA2 and/or IA3 due to potential need for internal business decision making or external briefing documents (Section 6.5). • Clarified definition of baseline UPCR in case of scenario where Week -1 values were missing (Section 3.1.1).

			
• CCI [REDACTED]• Updated study objectives and study design to align with current protocol (Section 2.1.3 and 2.2) and removed any mention of “Part B”.• Clarified minor points for individual profile plots (Section 6.1.1.1).• Updated demographic tables as required for IA readouts (Sections 6.4.2 and 6.4.3).• Note: Minor formatting issues were identified during QC performed after 22 Dec 2020 final draft version and were the only edits incorporated after database snapshot for IA1.• Included clinical output assessments, PK, ADA/Nab.
--	--	--	---

[figure not shown]
NOTE: *Italicized* text within this document has been taken verbatim from the Protocol Amendment 5.

2. INTRODUCTION

This SAP provides the detailed methodology for summary and statistical analyses of the data collected in study C0221002.

2.1. Study Objectives

2.1.1. Primary Objective

[figure not shown]
Primary Objective(s):	Primary Endpoint(s):

 • To evaluate the efficacy of PF-06730512 compared to baseline in the reduction of proteinuria following 12 weeks of treatment in patients with FSGS. 	
 • Percentage change from baseline to Week 13 in Urinary Protein to Creatinine Ratio (UPCR), calculated from the 24-hour urine collection.
Secondary Objective(s):	Secondary Endpoint(s):

 • To evaluate the safety and tolerability of PF-06730512 following up to 24 weeks of treatment in subjects with FSGS. • To evaluate the effects of PF-06730512 on proteinuria time course. • To evaluate the effect of PF-06730512 on renal function. • To evaluate the serum exposure of PF-06730512 in FSGS patients. • To evaluate the immunogenicity profile of PF-06730512. 	
 • Adverse Events, Laboratory Safety Tests (Hematology, Clinical Chemistry, Urinalysis), Body Weight, Blood Pressure, Pulse Rate, Body temperature and Electrocardiogram (ECG). • Percentage change from baseline to Weeks 2, 5, 9, and beyond Week 13, as applicable, in UPCR. • Percentage change from baseline to Weeks 3, 5, 9, 13 and beyond as applicable, in estimated glomerular filtration rate (eGFR). • Serum concentration of PF-06730512. • Incidence of the development of anti-drug antibody (ADA) and neutralizing antibody (NAb).
CCI 	

2.2. Study Design

The adaptive study consists of a Screening Period of up to 43 days, an approximately 8-week Lead-in Period, an Investigational Treatment Period of up to 24 weeks during which subjects will receive PF-06730512 once every 2 weeks (Q2W), followed by an approximately 9-week

[figure not shown]
Follow-up Period. Delays to the beginning of Lead-in or Investigational Treatment Period (up to 1 week from visit window specified) due to pending primary or repeat laboratory results that are submitted for analysis within the protocol specified window, will not be considered protocol deviations.

Figure 1. Schematic of the Study Design

Upon commencement of active treatment with PF-06730512, subjects will be dosed intravenously Q2W for up to 24 weeks, but the primary endpoint result will be based on UPCR from a 24-hour urine collection at Week 13. There will be a maximum of 12 infusions of PF-06730512 within the 24-week Investigational Treatment Period. Subjects enrolled prior to Amendment 5 of the protocol will be dosed for 12 weeks with a maximum of 6 infusions of PF-06730512 within a 12-week Investigational Treatment period. Telephone contact visits will be conducted the weeks in between dosing visits to check the subject's overall status, including new or worsening adverse events, changes to concomitant medications, compliance with appropriate contraceptive use, and reminders about upcoming urine collections, when applicable.

CCI

timepoints, according to the Schedule of Activities.

[figure not shown]
The duration of study participation will be up to approximately 11 months from Screening to the last post-treatment Follow-up Period visit. The durations of the study periods are listed below:

- Screening Period up to 43 days;
- Lead-in Period: approximately 8 weeks;
- Investigational Treatment Period: up to 24 weeks (up to 12 weeks for subjects enrolled prior to Amendment 5);
- Follow-up Period: approximately 9 weeks (after last dose given at visit Week 11 or 23).

3. ENDPOINTS AND BASELINE VARIABLES: DEFINITIONS AND CONVENTIONS

3.1. Primary Endpoint(s)

CCI

3.1.1. Percentage change from baseline to Week 13 in Urinary Protein to Creatinine Ratio (UPCR) based on 24-hour urine collection

The primary efficacy endpoint is the percentage change from baseline to Week 13 in the Urinary Protein to Creatinine Ratio (UPCR) based on 24-hour urine collections. UPCR will be calculated as urinary protein divided by the urinary creatinine value at the same collection time point. If a value of protein or creatinine is missing, UPCR will be missing for that respective value.

Baseline for the primary endpoint is defined as the Week -1 UPCR measurement that is based on the 24-hour urine collection. If the Week -1 24-hour UPCR value is not available, the nearest 24-hour UPCR measurement taken to the Week -1 visit will be used, provided it is pre-dose.

For sensitivity analyses utilizing first morning void UPCR assessments instead, the baseline is similarly defined as the Week -1 first morning void UPCR measurement. If the Week -1 first morning void UPCR value is not available, the nearest first morning void UPCR measurement taken to the Week -1 visit will be used, provided it is pre-dose.

Log-transformed change from baseline (i.e. the difference in \log_e -transformed values) will be the dependent variable in the analysis models. The results from the analysis models will be back-transformed to obtain the ratio to baseline. The percentage change from baseline will be derived by transforming the ratio using the following formula:

$$\text{Percentage change from baseline} = 100 * ([\text{back-transformed LSMean}] - 1)$$

For descriptive summaries, percentage change from baseline will be calculated as the Week 13 measurement minus the baseline value divided by the baseline value multiplied by 100.

3.2. Secondary Endpoint(s)

3.2.1. Percentage change from baseline to Weeks 2, 5, 9, and beyond Week 13, as applicable, in Urinary Protein to Creatinine Ratio (UPCR)

The secondary efficacy endpoints include percentage change from baseline to Weeks 2, 5 and 9 in UPCR based on both the 24-hour urine collections and the first morning voids. All analyses and descriptive summaries will report first morning void assessments and 24-hour urine assessments of UPCR separately. Descriptive statistics will be used to summarize UPCR by dose and timepoint for all timepoints in the Lead-in Period and the Investigational Treatment Period, as well as Week 13 data for subjects enrolled prior to amendment 5 and Week 25 data for subjects enrolled after amendment 5.

For descriptive summaries, percentage change from baseline will be calculated for each post-baseline measurement based on the respective urine collection, as that measurement minus the baseline value divided by the baseline value multiplied by 100.

3.2.2. Percentage change from baseline to Weeks 3, 5, 9, 13 and beyond, as applicable, in estimated glomerular filtration rate (eGFR)

The secondary efficacy endpoints of percentage change from baseline in estimated glomerular filtration rate (eGFR) include Weeks 3, 5, 9 and 13. Descriptive statistics will be used to summarize eGFR by dose and timepoint for all timepoints in the Lead-in Period and the Investigational Treatment Period, as well as Week 13 data for subjects enrolled prior to amendment 5 and Week 25 data for subjects enrolled after amendment 5.

The eGFR will be calculated based on the Chronic Kidney Disease Epidemiology Collaboration (CKD-EPI) formula¹ (see Appendix 4).

Baseline is defined as the Week -1 measurement. If the Week -1 eGFR measurement is not available, the nearest eGFR measurement taken to the Week -1 visit will be used, provided it is pre-dose.

Log-transformed change from baseline will be the dependent variable in the analysis models. The percentage change from baseline will be calculated for each post-baseline measurement, as that measurement minus the baseline value divided by the baseline value multiplied by 100.

3.2.3. Serum concentration of PF-06730512

Blood samples (approximately 3 mL whole blood) to provide a minimum of 1 mL of serum for pharmacokinetic (PK) analysis will be collected into appropriately labeled tubes at times specified in the Schedule of Activities section of the protocol.

Serum PK parameters will be derived, if data permits, from the concentration-time data using standard noncompartmental methods of analysis as outlined in Table 1. Actual PK sampling times will be used in the derivation of PK parameters when available. In the case that actual PK sampling times are not available, nominal PK sampling time will be used in the derivation of PK parameters.

Table 1. Serum PF-06730512 PK Parameters Definitions

[figure not shown]
Parameter	Definition	Method of Determination
AUC_{tau}	Area under the concentration-time profile from time zero to time tau (the dosing interval)	Linear/Log trapezoidal method.
$AUC_{\text{tau}}(dn)$	Dose normalized AUC_{tau}	$AUC_{\text{tau}}/\text{Dose}$
C_{max}	Maximum observed plasma concentration	Observed directly from data
$C_{\text{max}}(dn)$	Dose normalized maximum plasma concentration	$C_{\text{max}}/\text{Dose}$
T_{max}	Time to reach C_{max}	Observed directly from data as time of first occurrence
$t_{\frac{1}{2}}$	Terminal elimination half-life	$\text{Log}_e(2)/k_{\text{el}}$, where k_{el} is the terminal phase rate constant calculated by a linear regression of the loglinear concentration-time curve. Only those data points judged to describe the terminal loglinear decline will be used in the regression.
$CL/$	Clearance	$\text{Dose}/AUC_{\text{tau}}$
	Volume of distribution at steady state	$\text{Dose}/(AUC_{\text{tau}} \cdot k_{\text{el}})$

- If data permits

[figure not shown]
[figure not shown]
[figure not shown]

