- f. Two PK samples will be collected: 1 sample at pre-dose (within 30 minutes prior to dosing), and 1 sample at the end of infusion (within 6 minutes after the end of infusion) on Days 1 and 71 (Week 11) and 155 (Week 23).
- g. Only pre-dose PK samples will be collected on Weeks 3, 5, 7, 9, 13, 15, 17, 19, and 21 (within 30 minutes prior to dosing)
- h. Cytokines are collected at pre-dose (within 30 minutes prior to dosing), and 1, 2 and 4 hours post beginning of infusion ±15 minutes. Extra blood samples for cytokine measurements should be taken immediately if a subject develops symptoms typical for an infusion reaction during the IP administration.
- i. Subject who prematurely withdraws during Investigational Treatment Period (Week 1 through Week 24) should return for an Early Withdrawal/Termination visit and then enter into the Follow-up Period.
- j. The 24-Hour and FMV urine collections are to be obtained from subject at follow-up Screening Visit (Screening Visit 2).
- k. Telephone contact: Approximately 7 days after IP administration (±3 days at Weeks 4, 6, 8, 10, 12, 14, 16, 18, 20, 22, and 24) the subject will be contacted by telephone to discuss concomitant medications, contraceptive use and any new or changing adverse events. Subjects should also be reminded to collect urine samples as required and to bring the full containers back to site at the next visit (see footnote o below).
- l. On IP administration days, 12-lead ECGs are done pre-dose and at the end of infusion, within an approximately 45-minute window.
- m. The urine drug test at Screening is performed by the central lab.
- n. Blood sample for serum β-HCG are collected for central lab testing (in females of child-bearing potential, Screening Visit 2, Weeks -8, -1, 25, 29 and 33). On all IP administration days, serum for pregnancy tests via test strip as a stat procedure performed locally at the site, with the negative result being available prior to the administration of IP (Weeks 1, 3, 5, 7, 9, 11, 13, 15, 17, 19, 21 and 23).
- o. Site personnel to call subject **prior to** the upcoming visit to remind the subject to perform FMV and a 24-hour urine collection, explain how to correctly collect and to bring the full FMV and 24-hour urine containers to the site at their scheduled study visit. ***This call is critical before Week -1, Week 13 and Week 25 and Week 33 Visits, or any Early Termination visits.*** This call may be part of the Telephone contact calls, when applicable.

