1.2.5.2. Pharmacokinetics

[figure not shown]
In healthy non-Japanese subjects, C_{max} was observed shortly after the end of the infusion (median time for C_{max} [T_{max}] range of approximately 2.1 to 3.0 hours after the start of a 2-hour infusion) following single IV administration of PF-06730512 CCI

Serum concentrations post C_{max} exhibited a biphasic decline over time. Mean terminal halflife- ($t_{1/2}$) ranged from 5.3 to 13 days with a shorter $t_{1/2}$ observed at the lower doses, probably due to sensitivity limitation of the bioanalytical assay, ie, lack of quantifiable concentrations at later time points at lower doses. The geometric mean clearance (CL) values ranged between 0.034 to 0.054 L/hr across the doses and geometric mean volume of distribution at steady state (V_{ss}) values ranged from 9.3 to 14 L. CCI

CCI

CCI

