3.1. The Main Study to Assess PF-06730512

The adaptive study consists of a Screening Period of up to 43 days, an approximately 8-week Lead-in Period, an Investigational Treatment Period of up to 24 weeks during which subjects will receive PF-06730512 once every 2 weeks (Q2W), followed by an approximately 9-week Follow-up Period. Delays to the beginning of Lead-in or Investigational Treatment Period (up to 1 week from visit window specified) due to pending primary or repeat laboratory results that are submitted for analysis within the protocol specified window, will not be considered protocol deviations. Any such delays should be documented and brought to the Sponsor's attention immediately.

CCI

whilst the study is ongoing to determine futility of any evaluated dose, as well as determine which dose level will be evaluated next (see [Section 9.6](#)). Cohorts will be enrolled in sequence, but depending on the timing and the results of the pre-specified formal interim analyses, as well as the status of enrollment, the optional Cohort 3 may be initiated prior to (or instead of) the start and/or completion of Cohort 2. Any change from one cohort to another will be communicated formally to all investigators, along with the specific dose of PF-06730512 for that given cohort.

Figure 1. Schematic of the Study Design

Subjects will be seen at Screening (2 Screening Visits) and at Weeks -8, -4 and -1 during the Lead-in Period prior to Day 1 (start of PF-06730512 treatment). Subjects in the Lead-in Period will be eligible for transition to active treatment if at Week -1 the UPCR and eGFR meet eligibility criteria, as described in [Section 4.3](#).

Upon commencement of active treatment with PF-06730512, subjects will be dosed intravenously Q2W for up to 24 weeks, but the primary endpoint result will be based on UPCR from a 24-hour urine collection at Week 13. There will be a maximum of 12 infusions of PF-06730512 within the 24-week Investigational Treatment Period (starting at Day 1/Week 1 and at Weeks 3, 5, 7, 9, 11, 13, 15, 17, 19, 21, and 23 respectively). Telephone contact visits will be conducted the weeks in between dosing visits to check the subject's overall status, including new or worsening adverse events, changes to concomitant medications, compliance with appropriate contraceptive use, and reminders about upcoming urine collections, when applicable.

[figure not shown]

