IP	investigational product
IRB	institutional review board
IRC	internal review committee

Abbreviation	Term
IRT	interactive response technology
IUD	intrauterine device
IV	intravenous
IWR	interactive web response
K ₂ EDTA	dipotassium ethylenediaminetetraacetic acid
Kg	Kilogram
LFT	liver function test
LOCF	last observation carried forward
LSLV	last subject last visit
LSMeans	least squares mean
MAD	multiple ascending dose
MCH	mean corpuscular hemoglobin
MCHC	mean corpuscular hemoglobin concentration
MCV	mean corpuscular volume
MMF	mycophenolate mofetil
MMRM	mixed effects model of repeated measures
CCI	
N/A	not applicable
NAb	neutralizing antibody
NOAEL	no observed adverse effect level
PACL	Protocol Administrative Changes and Clarifications
PCD	primary completion date
PD	pharmacodynamics(s)
PGIS	Patient Global Impression of Severity
PI	principal investigator
PK	pharmacokinetic
PMDA	Pharmaceuticals and Medical Devices Agency
PP	per protocol
PR	pulse rate
Prep B1	K2EDTA plasma collection optimized for biomarker/proteomic/metabonomic analysis
Prep D1	dipotassium edetic acid
PT	prothrombin time
q.o.d.	every other day
Q2W	every 2 weeks
QTc	Corrected QT Interval
QW	every week
RAAS	renin-angiotensin-aldosterone system
RBC	red blood cell
RNA	ribonucleic acid
ROBO2	roundabout guidance receptor 2
SAD	single ascending dose
SAE	serious adverse event

Abbreviation	Term
SAP	statistical analysis plan
SC	subcutaneous
SF-12	12-Item Short Form Survey
SIQ	Symptom Impact Questionnaire
SLIT	slit guidance ligand
SLIT2	slit guidance ligand 2
SLIT2-N	slit guidance ligand 2, N-terminal fragment SLIT2-N
SOP	standard operating procedure
SRSD	single reference safety document
SUSAR	suspected unexpected serious adverse reaction
Sym-D	symptom diary
TBili	total bilirubin
TEAE	treatment-emergent adverse events
TNF- α	tumor necrosis factor-alpha
CCI	
ULN	upper limit of normal
UPCR	urine protein-to-creatinine ratio
US	United States
VHP	Voluntary Harmonization Procedure
Vz/F	apparent volume of distribution
WBC	white blood cell
WFI	water for injection
WOCBP	women of child-bearing potential

CCI

A series of 12 horizontal black bars of varying lengths, decreasing from left to right. The bars are set against a white background. The lengths of the bars are approximately: 1. 100%, 2. 90%, 3. 75%, 4. 60%, 5. 50%, 6. 40%, 7. 30%, 8. 25%, 9. 20%, 10. 15%, 11. 10%, 12. 5%.

[REDACTED]

[REDACTED]

[REDACTED]

CCI

[REDACTED]

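### SAP 3.2.3 labels a volume as steady-state (Vss in Table 4) but gives the formula for the terminal-phase volume, Vz

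*SAP*

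**What the plan says.** The parameter table in SAP 3.2.3 gives CL as Dose/AUCtau. Its last row is "Volume of distribution at steady state", computed as Dose/(AUCtau × kel). The half-life row defines kel: it "is the terminal phase rate constant calculated by a linear regression" of the log-linear part of the curve. The symbol cell of the volume row is blank in the public text. However, SAP 6.2.3.2 says the parameters of Section 3.2.3 are the ones summarised in Table 4, and Table 4 lists CL and Vss together.

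In Table 4, the AUCtau/Cmax row and the Tmax row carry Day 1 and Day 71. The row with CL and Vss shows no day, and neither does the half-life row.

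Protocol 1.2.5.2 says that in the first-in-human study serum concentrations after the peak "exhibited a biphasic decline over time". It gives a mean terminal half-life of 5.3 to 13 days and a geometric mean CL of 0.034 to 0.054 L/hr. Geometric mean Vss "values ranged from 9.3 to 14 L". It explains the shorter half-lives at lower doses as "probably due to sensitivity limitation of the bioanalytical assay".

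**The concern.** The label and the formula name different quantities. Noncompartmental Vss is CL × MRT, and neither MRT nor AUMC appears in the SAP table. CL/kel is Vz. The two agree only if the drug follows one-compartment kinetics, which the protocol's own description rules out.

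A programmer following the SAP would therefore produce a terminal volume, and the study report would print it as Vss. The protocol uses that name for the healthy-volunteer volume of 9.3 to 14 L, so a reader might set the two side by side and take a difference of definition for a difference between populations.

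A second, smaller gap is that the SAP does not say which day's AUCtau feeds CL and the volume. Dose/AUCtau equals CL only at steady state.

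**Working it through.** **1. Algebra.** With CL = Dose/AUCtau, Dose/(AUCtau × kel) = CL/kel = CL × t½/ln 2 = Vz. No data are needed for this step.

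**2. Scale from the protocol's ranges.** CL × t½ × 24/ln 2, in litres:

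| t½ (days) | CL 0.034 L/hr | CL 0.054 L/hr |
|---|---|---|
| 5.3 | 6.24 | 9.91 |
| 8 | 9.42 | 14.96 |
| 10 | 11.77 | 18.70 |
| 13 | 15.30 | 24.31 |

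The stated Vss is 9.3–14 L. The corners of this table may mix doses, so they bound a range and estimate nothing.

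**3. Vz/Vss with exact data.** The ratio is (1/kel)/(Vss/CL), so no central volume is needed. I assume low CL goes with low Vss and high with high:
- Vss/CL = 9.3/0.034 = 273.5 h = 11.40 days
- Vss/CL = 14/0.054 = 259.3 h = 10.80 days

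| t½ (days) | 1/kel (days) | Low pair | High pair |
|---|---|---|---|
| 8 | 11.54 | 1.01 | 1.07 |
| 10 | 14.43 | 1.27 | 1.34 |
| 13 | 18.76 | 1.65 | 1.74 |

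At 5.3 days the ratios are 0.67 and 0.71. Vz cannot be below Vss, so that half-life does not belong with these pairs. The ratio reaches 1 at 7.9 and 7.5 days.

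**4. Effect of the sparse Day 71 interval.** Footnotes f and g of the Schedule of Activities give a Day 71 pre-dose sample, one within 6 minutes of the end of infusion, and then the Week 13 sample 14 days later. A log trapezoid between the last two spans both phases of the decline and overstates AUCtau.

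To see how much, take a two-exponential curve with MRT = Vss/CL and terminal rate β. The distribution rate α is not in the documents; I assume distribution half-lives of 0.5, 1 and 2 days. The terminal share of AUC is f = (MRT − 1/α)/(1/β − 1/α).

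Worked case: high pair, t½ 10 days, distribution half-life 1 day.
- f = (10.80 − 1.44)/(14.43 − 1.44) = 0.72
- In units where true steady-state AUCtau is 1, the concentration after the sixth 1-hour infusion is 0.271 at its end and 0.0305 at 14 days.
- Log trapezoid: (0.271 − 0.0305)/ln(0.271/0.0305) × 14 ≈ 1.54
- Printed volume/true Vss = 1.34/1.54 ≈ 0.87

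Printed volume/true Vss over both pairs and half-lives of 8, 10 and 13 days, with kel taken as exact:

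| Assumed distribution half-life (days) | Range |
|---|---|
| 0.5 | 0.62–0.94 |
| 1 | 0.86–0.98 |
| 2 | 1.00–1.36 |

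**5. Why the day matters.** Doses are given "starting at Day 1/Week 1 and at Weeks 3, 5, 7, 9, 11" and later, so Day 71 is the sixth dose. Its AUCtau is short of steady state by at most 2^(−84/13) = 1.1%, before sampling error. On Day 1, the share of single-dose AUC lying beyond 14 days can be as high as 2^(−14/5.3) = 16% at a half-life of 5.3 days and 2^(−14/13) = 47% at 13 days. These are one-compartment ceilings.

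**The case against.** The mismatch itself is hard to contest. One could read the label as a terminal volume calculated from steady-state data, but the symbol Vss in Table 4 and the protocol's use of Vss count against that. The objections to anything larger are good ones.

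- **Inflation of up to 74%.** A reader might infer that the reported volume will be too high by that much. The documents do not support it. The figure assumes an exact AUCtau, and the overstated Day 71 AUCtau pulls the other way. It also rests on an assumed pairing, and sets a half-life described only as a mean against geometric means of CL and Vss. All inputs come from healthy volunteers.
- **Day 1 values.** A reader might infer that CL and the volume will come from Day 1 and be overstated. The SAP nowhere says so. It calls for standard noncompartmental methods, under which Dose/AUCtau is the steady-state formula. The half-life row has no day either, which fits a convention for once-per-subject parameters, and the table layout may be broken in the public text. Only a request for clarification stands.
- **A false patient–volunteer difference.** No visible passage plans that comparison, and none says how the first-in-human Vss was computed. If the same formula was used there, the label would be wrong in both but the values comparable.
- **The abbreviation list.** Protocol Appendix 1 has Vz/F ("apparent volume of distribution") and no Vss entry. That shows little, since Vss is defined in the text of 1.2.5.2.

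The derivation is also conditional on the data permitting it. That limits how often the problem arises, but whenever the parameter is derived it carries the wrong name.

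**Conclusion.** The point holds as a labelling error: the stated rule returns Vz and the table calls it Vss. This part is certain because it follows from the SAP's own definitions. That the two volumes differ for this drug rests on the reported biphasic decline.

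The size is less certain. With exact data and the assumed pairing, Vz exceeds Vss by about 1–7% at a half-life of 8 days and 65–74% at 13 days. With the planned Day 71 sampling the printed value could be below or above true Vss (0.62 to 1.36 times under the assumed distribution half-lives). I would not quote any figure as the expected error.

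Severity is minor. The serum concentration endpoint, the decision criteria and the primary UPCR analysis do not use this parameter.

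**What to change.** In SAP 3.2.3 and Table 4, do one of two things:
- keep the formula and rename the parameter Vz; or
- keep Vss and define it as CL × MRT, to be reported only where sampling supports an MRT.

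Renaming is the safer choice given the sparse profile. As a clarification, state in Table 4 that CL and the volume use Day 71 AUCtau and not Day 1. Add a footnote that Day 71 AUCtau rests on two post-dose concentrations and is likely overstated.

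The cost is a few words in two tables and one footnote, with no new samples or models. The only thing given up is a Day 1 CL or volume in the study report.
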